7.4 Follow-up Safety Contact One Week After FV

The COHS will contact the parent/caregiver of each child who received FV 3-10 business days after administration to inquire if the child had any adverse reaction, and/or required any unscheduled (urgent or emergent) health care consultation or visit. If the child had a reaction or required a health care consultation or visit, information regarding the encounter will be documented on the adverse event form and the PI will be notified.

7.5 Final Study Visit

The final study visit will be the third year follow-up evaluations of the children and the final parent/caregiver questionnaires.

7.6 Early Termination Visit

No early termination visits are anticipated.

7.7 Unscheduled Visit

No unscheduled visits are anticipated.

8 STUDY PROCEDURES/EVALUATIONS

8.1 Clinical Evaluations

All children in the study will be provided an oral health screening at baseline and annually thereafter for 3 years (up to 4 screenings total). The oral health screening will collect dmfs measures (objective 3.1.1.3 and 3.1.2.1/ outcome 3.2.1 and 3.2.2.1) of the children, to be completed by calibrated dental hygienists who will visit each HSC in both the COHS intervention (Group 1) and usual care (Group 2) arms. Procedures for the oral health screening will be followed according to the protocol of the Caries Outcome Work Group of the ECC consortium. The Caries Outcome Work Group will develop an SOP for the oral health screenings, which will be attached to this protocol. The criteria for the determination of dmfs measures according to Drury, et al.²⁸ will be used. These criteria include the counting of both non-cavitated and cavitated carious lesions.

8.2 Laboratory Evaluations

8.2.1 Clinical Laboratory Evaluations

There will be no clinical laboratory evaluations in the study.

8.3 Specification of Safety Parameters

Safety parameters will include any serious adverse events (SAEs) or any unanticipated problems involving risk (UPs) that occur with general participation in the COHS program. Adverse events related to the topical application of FV will be collected for 3-10 days following each application (refer to section 7.4).

8.4 Methods and Timing for Assessing, Recording, and Analyzing Safety Parameters

8.4.1 Adverse Events

ICH E6 defines an adverse event (AE) as any untoward medical occurrence in a patient or clinical investigation subject administered a pharmaceutical product regardless of its causal relationship to the study treatment. An AE can therefore be any unfavorable and unintended sign, symptom, or disease temporarily associated with the use of medicinal (investigational) product including anaphylaxis, oral discomfort, or oral disfigurement. In this study, due to the

anticipated low risk of the intervention, AEs that do not meet the reporting criteria parameters for medically attended events, SAEs or UPs will not be collected.

All medically attended, or medically treated AEs, or circumstances where parent or guardian contacted health care provider for advice regarding AE for this time period will be reported on an AE form. This would exclude an upset stomach or runny nose that required no treatment or health care provider contact in addition to bumps and bruises treated at home. Medically attended events will be captured in a 3-10 day window after FV administration. SAEs and UPs will be captured throughout the study period.

All AEs will be graded for severity and relationship to the study product. Severity may be graded based on the following scale: mild, moderate, severe, life-threatening, death (CTCAE criteria: http://ctep.cancer.gov/protocolDevelopment/electronic_applications/ctc.htm)

Relationship to Study Products: The clinician's assessment of an AE's relationship to the test article will be a part of the documentation process, but it will not be a factor in determining what is or is not reported. If there is any doubt as to whether a clinical observation is an AE, the event will be reported. All AEs will have their relationship to the study product assessed using the terms: associated or not associated. In a clinical trial, the study product must always be suspected. To help assess the relationship of the AE to the study product, the following guidelines will be used:

1. Expected (Associated) Adverse Event: An adverse event that is consistent in the nature or severity with the applicable product information (e.g., Investigator Brochure)
2. Unexpected (Not Associated) Adverse Event: An adverse reaction, the nature of severity of which is not consistent with the applicable product information

The subject with a medically attended AE will be contacted by the PI and/ or the study doctor/dentist via ~~telephone~~ **telephone** or in person for a safety follow-up within one week after FV administration and documentation of the AE. Information will be collected on any medically attended visits for cause.

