7.3 Follow-up Visits for FV

The applications of FV for HS children and OHP will be delivered in the HSCs by the COHS (Group 1). FV will be offered 4x a year for 2 years to children in the classroom on the scheduled day; multiple attempts will be made to provide FV to children not in the classroom on the scheduled day. Group 2 participants will receive usual oral health care made available by the IHS Dental providers (or other dental providers outside the reservation).

Annual dmfs measure of the children, and parent ACASI survey to collect dental knowledge, attitudes, and behaviors will take place annually for 3 years. We will follow the families whose children age out of Head Start and make arrangements for them to complete the child oral health screening and parent ACASI survey at a convenient time and location. All annual follow-up assessments will be done as near as possible to the anniversary of the previous year's oral health screening at that HSC, with the goal of completing them within a month either side of that date.

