8.4.2 Serious Adverse Events (SAEs) and Unanticipated Problems (UPs)

A serious adverse event (SAE) is an AE that, in the view of *the investigator or sponsor*, results in any of the following outcomes:

1. Death
2. Life-threatening event

-
- The decision is based on the investigator's opinion. Must place the subject at immediate risk of death. Example: Anaphylaxis. An adverse event that, had it occurred in a more severe form, might have caused death
3. An event requiring inpatient hospitalization or prolongation of existing hospitalization. This excludes any planned hospitalizations for elective procedures that are not related to study participation.
 4. A persistent or significant incapacity or substantial disruption of the ability to conduct normal life functions
 5. A congenital anomaly/birth defect subsequent to the administration of the agent
 6. An important medical event that may not result in death, be life-threatening, or require hospitalization, but may be considered serious that, based upon appropriate medical judgment, may jeopardize the patient or subject and may require medical or surgical intervention to prevent one of the outcomes listed above

Note on inpatient hospitalization and prolongation of hospitalization: Subject must be hospitalized for more than 24 hours. Going to the hospital for observation does not meet the definition of hospitalization. Emergency room visits that do not result in an admission to the hospital should be evaluated for one of the other serious outcomes (e.g. life-threatening, required intervention to prevent permanent damage; other serious medically important event).

All related SAEs occurring at any time during the 2-year treatment and additional year of follow-up will be reported to NIDCR via the CROMS contractor, as well as to COMIRB and NNHRRB within 72 hours of receipt of information about the SAE. All SAEs will be recorded on the appropriate SAE CRF, be followed through to resolution or stabilization by a study clinician, and be reviewed and evaluated by a study clinician.

An unanticipated problem involving risks to the subjects or to others (UP). This would be any incident, experience, or outcome that meets all of the following criteria:

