8.7 Halting Rules

The frequency of AEs meeting criteria defined in protocol Section 8.4.1 in this study is expected to be very small. If the number of SAEs is large, or of a particular type, NIDCR and the Data and Safety Monitoring Board may consider temporarily suspending enrollment and/or the FV interventions until a safety review is convened. The objective of the safety review would be to make a decision on whether the study should continue per protocol, proceed with caution, be further investigated, be discontinued, or be modified and then continued.

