14.3 Types of Data

Data stored in paper format include consent and HIPAA documents, and program evaluation forms. Electronic data include information as part of the primary and secondary outcome measures of the study; demographic information, questionnaires related to dental knowledge, attitudes, beliefs, and practices, child use of dental and medical service for oral health problems, parent time and travel costs associated with the intervention and obtaining services; and program intervention costs.

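### SAE capture is promised for the whole study, but the only contact specified to ask about health events follows varnish in Group 1; in Group 2, and in both arms in year 3, capture is passive

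*Combined protocol and SAP*

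**What the plan says.** Section 8.4.1 commits to study-long capture: "SAEs and UPs will be captured throughout the study period". Section 8.4.2 says that every SAE is to go on the SAE form and be followed up by a study clinician, and sets the reporting period: "All related SAEs occurring at any time during the 2-year treatment and additional year of follow-up will be reported to NIDCR". Section 8.5.2 has field staff pass all SAEs and UPs to the principal investigator within 24 hours of hearing of them, and the investigator pass all SAEs to the sponsor within 72 hours.

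The contact specified to ask parents about reactions and urgent care is in section 7.4: "The COHS will contact the parent/caregiver of each child who received FV 3-10 business days after administration". Medically attended events are tied to a similar period: "Medically attended events will be captured in a 3-10 day window after FV administration". Varnish is a Group 1 treatment, and section 7.3 gives its frequency: "FV will be offered 4x a year for 2 years to children in the classroom on the scheduled day".

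Section 8.3 describes the safety parameters as SAEs and UPs "that occur with general participation in the COHS program".

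Both arms have an annual oral health screening and an annual parent survey through year 3 (sections 7.3, 8.1 and 14.4). Section 14.3 lists the service-use data as "child use of dental and medical service for oral health problems".

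**The concern.** The capture period and the means of capture do not match. The commitment covers three years and is not limited to one group, but the only specified enquiry follows a product that one group receives for two years. A hospital admission in a Group 1 child shortly after varnish should come to light because someone asks. The same admission in a Group 2 child, or in any child in year 3, is recorded only if someone volunteers it.

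If SAE counts by arm are then set side by side, in reports to the DSMB or in the final results, a difference between arms cannot be separated from a difference in who was asked. A low Group 2 count would not be a usable background rate. The primary dmfs result is not affected.

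**Working it through.** The plan states no figure on this point, so there is none to reproduce. The check sets each scheduled contact after baseline against the stated capture period.

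| Contact | Group 1, years 1-2 | Group 1, year 3 | Group 2, years 1-2 | Group 2, year 3 |
|---|---|---|---|---|
| Post-varnish contact asking about health events (7.4) | up to 8 | 0 | 0 | 0 |
| 15-minute observation after varnish (6.2) | up to 8 | 0 | 0 | 0 |
| COHS classroom activities and parent events (14.4) | 4 and 3 a year | none described | none described | none described |
| Annual screening and parent survey (7.3, 8.1) | 2 | 1 | 2 | 1 |

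Only the last row is the same in both arms, and neither of its parts is described as asking about SAEs. Chance reporting is also likely to be unequal, because Group 1 families meet study staff more often (third row).

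**Contacts per child.** Group 1: 4 a year x 2 years = 8 at most. Group 2: 0. Section 4 says that the number of interventions varies with time spent in Head Start, so some Group 1 children will have fewer than 8.

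**Child-years.** Section 10.2 plans 520 children per group. With three years of follow-up for all:
- total: (520 + 520) x 3 = 3120
- in periods with scheduled post-varnish contacts: 520 x 2 = 1040
- in periods with none: 3120 - 1040 = 2080, and 2080/3120 = 67%

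**Days covered.** Section 7.4 counts business days, while sections 8.3, 8.4.1 and 8.5.3 say days. I therefore assume that each contact covers 10 to 14 calendar days after varnish, out of 3 x 365 = 1095 days.
- 8 applications: 8 x 10 = 80 days (7.3%) to 8 x 14 = 112 days (10.2%)
- 4 applications: 4 x 10 = 40 days (3.7%) to 4 x 14 = 56 days (5.1%)
- Group 2: 0%

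**Scope, section by section.**
- 8.3 refers to participation in the COHS program, which reads as Group 1.
- 8.4.1 has no limit by group.
- 8.4.2 records all SAEs, but its sentence on the reporting period sends only *related* ones to the sponsor.
- 8.5.2 sends all SAEs to the sponsor.

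Taken together, these do not settle whether an unrelated hospital admission in a Group 2 child is to be reported.

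**The case against.** **Capture is passive, not absent.** A reader might infer that no SAE in Group 2 or in year 3 would ever be found. The documents do not support that. Section 8.5.2 gives a study-wide reporting route, and the annual screening and survey bring staff into contact with both arms through year 3. The survey might reveal a serious oral health event. Its items are not shown: section 4 says service utilization without restriction, and section 7.2 includes health history at enrollment. The restriction to dental care or oral health problems comes from sections 6.5, 10.4 and 14.3. This objection stands against the stronger reading. It does not supply a question about SAEs or a link from the survey to an SAE form.

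**Scope may be narrower than it looks.** Section 8.4.1 defines an adverse event in terms of a subject given a product, and a UP must be at least possibly related to the research. On that wording, events in untreated children might be out of scope. Section 8.3 also says that the parameters *include* these events, which is not exclusive. But recording and reporting all SAEs points the other way, so the sections still need reconciling.

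**The halting rule is not comparative.** A reader might infer that section 8.7 cannot be applied without a Group 2 rate. Its trigger is "If the number of SAEs is large, or of a particular type", which the DSMB can judge without a between-arm test. Section 10.4 plans no between-arm SAE analysis either. Both points stand. The loss is in the meaning of arm-level counts, not in the ability to halt.

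**Low risk justifies light collection.** Section 8.4.1 scales collection to the anticipated low risk, and an enquiry soon after varnish suits the mainly acute reactions in section 2.3.1. That is a fair reason to leave minor events uncollected. It does not explain unequal capture of SAEs, which the plan says it will capture throughout.

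**Other documents may fill the gap.** The Manual of Procedures, the SAE form and the DSMB Charter are not among the documents. Any of them could hold an SAE prompt for both arms.

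**Conclusion.** The concern holds as a mismatch between a study-long commitment and an enquiry that exists in one arm for two years. Followed as written, the plan gives Group 1 up to 8 enquiries per child and Group 2 none, and leaves 67% of planned child-years in periods without one. SAE counts by arm would not be comparable, and the scope of reporting is stated inconsistently.

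The contact counts follow directly from the documents. The child-year figure assumes that all 1040 children are followed for three years, ignoring dropout and later enrollment. The day-coverage figures also rest on the assumed 10 to 14 days per contact.

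A reader might go on to infer a predictable spurious excess of SAEs in Group 1. The documents do not support a number: they give no SAE rate, and any such excess would depend on how much passive reporting finds in each arm.

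**What to change.** 1. Reconcile sections 8.3, 8.4.1, 8.4.2 and 8.5.2 so that they state that SAE and UP capture covers both groups for all three years, and say the same thing about whether all SAEs or only related ones go to the sponsor.
2. Add an identical SAE/UP question to the existing annual parent contact in both arms at years 1, 2 and 3, asking about the time since the last annual contact. It should cover every seriousness criterion in section 8.4.2, including incapacity and important medical events, not just death, life-threatening events and hospital stays. A positive answer triggers the existing SAE form, and UPs follow their existing route.
3. Keep the post-varnish contact. Report SAEs by arm and by source (post-varnish contact, annual question, volunteered), and base any between-arm comparison on the annual question alone.
4. If the Manual of Procedures or a case report form already contains such a question, cite it in section 8.4 instead of adding another.

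The cost is a few items on a contact already held in both arms, and no new visits. The drawbacks are 12-month parent recall, more unrelated events to process, and no information on children who do not return. On the 70% retention assumed in section 10.2, that last group could reach 0.30 x 520 = 156 children per group, so the reports should give the number of children asked in each arm.

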2.3 Potential Risks and Benefits

2.3.1 Potential Risks

Potential risks include disclosure of confidential information including oral health status, extent of oral disease, oral health knowledge, attitudes, and behaviors, and effect mediators or moderators. There is also the potential of psychological distress associated with the oral health screening and application of the FV with young children. Parents/caregivers and children will have the opportunity to terminate their involvement in the study at any time. Study staff will be trained in techniques to keep study data confidential. Patient identifying information will not be included in the research databases. Once data are collected, a research database will be created in which data are recorded using research ID numbers. All data will be stored on password-protected network drives, and paper copies of any data or consent forms will be kept in locked file cabinets.

Adverse reactions to the FV are extremely rare; particularly since dispensing of the FV and the single unit dosage delivered to each participant will be controlled. Adverse reactions may include temporary change in tooth color²⁷ or potential risk of contact allergy to the colophonium resin base if the varnish is applied to ulcerated gingival tissues. According to the FV package insert, edematous swelling has been reported only in rare instances, especially following application to extensive surfaces with FV. Though extremely rare, acute exacerbation of asthmatic conditions, or dyspnea, has occurred in asthmatic people. Nausea can occur in patients with known sensitive digestive systems, especially following extensive applications. More information is available from the FV MSDS form (*Appendix A*) attached. Intervention staff will be instructed to monitor children following fluoride application, recognize these adverse reactions and respond with prompt referral to the IHS dental clinic. After attending to urgent or emergent needs of the child, intervention staff will contact the study PI immediately to report the event and complete reporting requirements.

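### Section 8.4.1 gives expectedness as the only guide to rating relationship to the varnish, and sections 8.4.2 and 8.5.2 disagree on whether only related SAEs are reported to NIDCR

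*Combined protocol and SAP*

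**What the plan says.** **Rating of relationship (8.4.1).** The section sets a two-term scale: "All AEs will have their relationship to the study product assessed using the terms: associated or not associated". It then introduces its criteria: "To help assess the relationship of the AE to the study product, the following guidelines will be used". There are two:

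- "Expected (Associated) Adverse Event: An adverse event that is consistent in the nature or severity with the applicable product information"
- "Unexpected (Not Associated) Adverse Event: An adverse reaction, the nature of severity of which is not consistent with the applicable product information"

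Just before these, the section also says that the study product is to be suspected in every case. It calls the rating the clinician's assessment and says of it that "it will not be a factor in determining what is or is not reported".

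**Reporting of SAEs.** Section 8.4.2 states: "All related SAEs occurring at any time during the 2-year treatment and additional year of follow-up will be reported to NIDCR". The route is the CROMS contractor, the two IRBs (COMIRB and NNHRRB) are included, and the limit is 72 hours. The same section has every SAE entered on the SAE form and reviewed by a study clinician. Section 8.5.2 has the PI report all SAEs, with no limit to related ones, to NIDCR through the same contractor in the same 72 hours. It mentions the IRBs only for unanticipated problems (UPs).

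**Unanticipated problems (8.4.2).** A UP must be unexpected (criterion 1) and also related or possibly related to taking part in the research (criterion 2). It must also suggest a greater risk than was known.

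**The concern.** Relationship and expectedness answer different questions. Relationship asks whether the varnish caused the event. Expectedness asks whether the event is already described in the product information. Section 8.4.1 asks the first question and supplies criteria only for the second. Neither guideline refers to timing, plausibility or another cause.

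The case most exposed is a new reaction to the varnish, which is what a causality rating is there to pick out. The guidelines steer it to the label that says the varnish was not involved. The second guideline even applies that label to an adverse reaction, the term that section 2.3.1 uses for effects of the varnish ("Adverse reactions to the FV are extremely rare").

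The reporting rules add a second difficulty. If 'related' in 8.4.2 is taken to mean 'associated' in 8.4.1, the label could decide whether the IRBs receive the 72-hour report of a serious new reaction.

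**Working it through.** The plan gives no figure to reproduce, so the check is to trace the rules as written.

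**1. Pairings of expectedness and relationship.** Two levels of each give 2 × 2 = 4 possible pairings.

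| | Associated | Not associated |
|---|---|---|
| Expected | provided (guideline 1) | no place |
| Unexpected | no place | provided (guideline 2) |

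Two of the four are provided. The two missing ones are:

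- *Unexpected and associated.* A varnish-caused event outside the product information goes to 'not associated'. This error hides a possible signal.
- *Expected and not associated.* An event with another cause that matches a listed effect goes to 'associated'. This error is on the cautious side. A possible example comes from section 2.3.1: "Nausea can occur in patients with known sensitive digestive systems". If the product information lists nausea in that way, a child with a sensitive digestive system whose nausea came from an unrelated illness, and whose parent contacted a provider, would be labelled 'associated'. This is conditional, because section 2.3.1 is a summary and the package insert and Appendix A are not supplied.

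**2. Internal consistency of 8.4.1.** Suspecting the product in every case is at odds with a guideline that labels unlisted reactions as not associated.

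**3. Reporting rules side by side.**

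| Section | Which SAEs | To whom | Time |
|---|---|---|---|
| 8.4.1 | relationship does not decide reporting | not stated | not stated |
| 8.4.2 | related SAEs | NIDCR via CROMS, both IRBs | 72 hours |
| 8.5.2 | all SAEs | NIDCR via CROMS | 72 hours |
| 10.3.1 | SAEs, no limit to related ones | NIDCR Medical Monitor, from CROMS | 24 hours from the contractor's receipt |

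Sections 8.4.2 and 8.5.2 differ directly on NIDCR: same recipient, route and time, but different scope. Section 8.4.1 agrees with 8.5.2, though its sentence may concern only entry on the AE form. The word 'related' in 8.4.2 is therefore the outlier.

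**4. What depends on the label.** Whatever the label, SAEs go from the field to the PI within 24 hours and then to NIDCR (8.5.2), to the Medical Monitor (10.3.1), to clinician review (8.4.2) and to the DSMB in periodic reports (8.5.2, 10.3.1). The halting and safety-review provisions (8.7, 10.3.1) turn on the number, frequency, type or character of events. No efficacy analysis in 10.4 uses the label. The one duty that could depend on it is the 72-hour IRB report in 8.4.2, and only if 'related' there is read as 'associated'.

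**5. Scale.** Inputs: about 520 children in group 1 (10.2); varnish offered 4 times a year for 2 years (7.3). Planned applications: 520 × 4 × 2 = 4,160, approximately. The number given will differ, because section 4 says that the number of interventions a child receives varies with Head Start attendance. Nor does 4,160 bound the number of labelled events, because SAEs and UPs are captured throughout the study and not only in the windows after varnish. The plan gives no event rate; section 8.7 expects AEs to be very few.

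**The case against.** The strongest reply is that the guidelines only support a clinical judgement. A competent clinician, told to suspect the product always, would not call an obvious varnish reaction unrelated because the package insert omits it. The AE form and the Manual of Procedures may already separate the two items. All SAEs reach the PI, NIDCR, the Medical Monitor and the DSMB regardless. Both NIDCR rules can be obeyed together by following the wider one.

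Much of this stands, and it rules out several stronger readings that a reader might infer:

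- *Every new varnish reaction will be misrecorded.* Not supported. The clinician may depart from the guidelines, so the error is possible, not certain.
- *Sections 8.4.1, 8.4.2 and 8.5.2 all contradict one another.* Not supported. Sections 8.4.1 and 8.5.2 agree.
- *Serious reactions could go unreported, or no unexpected event could qualify as a UP.* Not supported. Nothing carries the 8.4.1 label into 8.4.2. UP criterion 2 is also wider, since it covers possible relation and concerns participation rather than the product.
- *The 4,160 applications are an upper bound on mislabelled events.* Not supported, for the reason given in the working.

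The reply does not remove the defect. The section says that the guidelines will be used and offers no other criterion. A form or manual that separated the items would then differ from the protocol. That one can comply with two rules by obeying the wider one does not make them consistent.

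**Conclusion.** The concern holds as a fault in the safety wording that should be fixed. Section 8.4.1 equates relationship with expectedness, so a rater who follows it would label an unlisted varnish reaction as not associated. Separately, 8.4.2 and 8.5.2 disagree on which SAEs go to NIDCR, and which SAEs go to the IRBs is left unclear.

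The size is limited. The number of affected events cannot be derived and is probably small, given the plan's own expectation of few AEs. The efficacy results are untouched. A missed 72-hour IRB report is possible only on a reading of 'related' that the documents do not state.

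Confidence is high for the wording itself. What happens in practice rests on the AE form, the Manual of Procedures and the product information, none of which is supplied.

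**What to change.** - In 8.4.1, replace the two guidelines with two separately recorded items: relationship to the study product, as a causal judgement (for example on timing, plausibility and other causes), and expectedness, judged against the product information.
- State that expectedness does not decide whether an SAE is related under 8.4.2 or whether a problem meets UP criterion 2.
- Reconcile 8.4.2 with 8.4.1 and 8.5.2, so that one rule says which SAEs go to NIDCR and which go to COMIRB and NNHRRB.

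The cost is revised wording in 8.4.1, 8.4.2 and 8.5.2 and, unless the AE form already separates the items, one added field. Sample size, outcome data and analyses do not change.
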